Randomization: We will use Block random assignment (blocks of 4 by each recruitment site) to ensure equal numbers are assigned to each condition by site. Randomization should create groups with equal characteristics with respect to disease related and medical variables. However, we will assess for baseline differences prior to conducting any analyses and control as necessary.

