10.0 Subject Population*

Participants will be 90 patients recruited through DOH Columbia County and CAN Community Health.

Study inclusion criteria includes that patients must be:

1. HIV-positive (seropositive confirmed by medical records).
2. Arrive for a clinic visit with an HIV physician.
3. Have a substance misuse screening score indicating moderate or high risk.

Persons will be ineligible if they:

1. are unable to interview and consent in English
2. unwilling or unable to participate in follow up
3. currently in addiction treatment
4. have a medical marijuana prescription

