Missing Data. We will handle missing data values with a 3-step process. First, the dropout rates will be compared across the groups with chi-square analyses to assess systematic differences due to condition. Second, demographic and dependent variables will be examined for their relationship to dropout. Those variables related to dropout status will be used to impute missing values for use in the analyses described (via SPSS Missing Items Analysis). Finally, comparison of the completers vs. imputation analyses will yield an additional estimate of the effect of dropouts on hypothesis tests.

Confidentiality Safeguards

PROTOCOL TITLE: Feasibility of Brief Intervention for HIV+ Adults 50+ in Primary Care Settings

To ensure confidentiality, all information will be coded so that it cannot be associated with any individual. A master sheet, with individual names and their respective code numbers will be kept in a locked file that can be accessed only under supervision of the PI. All data entered into the computerized database will be identifiable by subject code number only. No one outside of the lead research team will have access to records identifying participants' names at any time. The information gathered will be used only for scientific, educational, or instructional purposes.

Data Safeguards

Any computer files with identifying data, such as subject logs needed to match data to names over time, will be protected by multiple passwords. During the analysis of the data, all identifying information with the exception of the subject identification number is removed from the data.

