Attrition is a significant concern in an implementation trial. First, we will develop a strong collaborative relationship between participants and members of the research team. This is a critical component of our retention strategy, beginning at the moment of first contact between the recruiter and potential participant. Second, we will ensure that participants understand that they are making a contribution and that their efforts have the potential to improve other people's experiences. Participants will receive study newsletters and flyers containing useful and pertinent information on wellness management and other related resources and local events. Finally, we will obtain secondary contact information and will use multiple communication channels (email, phone, text messaging, social media) to maintain contact with study participants. We have budgeted research staff time for tracking and follow-up of participants. One RA will dedicate 20% time to patient tracking during recruitment and follow up phase. Based on our prior work using these strategies with this patient population, we anticipate a 10% dropout rate with a maximum dropout rate of 20% by time 3.

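### Imputation variables are picked by a weak dropout screen with no check within arms, so dropout that differs by arm could leave avoidable bias in the Aim 3 drug-use contrast

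*Protocol*

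**What the plan says.** Protocol section 17.0, Missing Data, has three steps.

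1. Rates by arm: "First, the dropout rates will be compared across the groups with chi-square analyses to assess systematic differences due to condition".
2. A screen: "Second, demographic and dependent variables will be examined for their relationship to dropout". The result sets the imputation model: "Those variables related to dropout status will be used to impute missing values for use in the analyses described".
3. A sensitivity comparison: "comparison of the completers vs. imputation analyses will yield an additional estimate of the effect of dropouts on hypothesis tests".

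No step asks whether a variable's link to dropout differs by arm. Neither arm nor the baseline value of the outcome is guaranteed a place in the imputation. No significance level is given for the screen. The SAP repeats the Aim 3 analysis but has no text on missing data.

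On the size of the problem, section 25.0 (Retention) says "we anticipate a 10% dropout rate with a maximum dropout rate of 20% by time 3".

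**The concern.** A variable belongs in an imputation model because it predicts the missing outcome, and above all if it also predicts who is missing. The plan selects on the second property alone, by a test with few dropouts behind it. Baseline drug use is likely to be among the best predictors of later drug use, yet it enters only if the screen happens to pick it up.

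The two checks also look past the pattern that matters for a comparison of arms. Step 1 asks whether the arms lose equal numbers. Step 2, on its plain reading, asks whether dropouts differ from completers overall. The Aim 3 contrast is distorted when the arms lose different kinds of patients, which can happen with equal rates and with little or no overall difference. At stake is a spurious shift in the drug-use contrast that data already collected at baseline could remove.

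**Working it through.** The documents give no power, SD or operating figure for these checks, so there is no stated figure to reproduce.

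**Inputs from the protocol.** Section 10.0: "Participants will be 90 patients recruited through DOH Columbia County and CAN Community Health". Section 6.0: "We will use Block random assignment (blocks of 4 by each recruitment site) to ensure equal numbers are assigned to each condition by site", hence 45 per arm. Dropout is 10% (9 of 90) to 20% (18 of 90).

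**Assumptions, not in the documents.** Screen at two-sided p<.05, the level section 17.0 uses for its covariate rule. Correlation ρ = 0.6 between baseline and 6-month use. Normal outcome, no true effect, equal dropout rates d in both arms. Dropout depends only on baseline use and arm, with a gap D of about 0.5 to 0.9 SD in baseline use between dropouts and completers. Missing values are filled by regression, with arm in the model.

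**Strength of the screen.** The noncentrality for a gap of 0.5 SD is 0.5 × √(n₁n₂/(n₁+n₂)), with 88 degrees of freedom.

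- 9 versus 81: 0.5 × √8.1 = 1.42, power 0.29.
- 18 versus 72: 0.5 × √14.4 = 1.90, power 0.47.

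The step 1 chi-square is no stronger: for 10% versus 20% dropout with 45 per arm its power is 0.28.

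**Bias when baseline use is left out.** Losing a fraction d whose mean is D above the completers moves the completers' baseline mean by −dD, and their outcome mean by −ρdD. If the arms move in opposite directions, the contrast is off by 2ρdD. If only one arm moves, it is off by ρdD. If both move alike, the shifts cancel. Multiplying by the proportion of trials that omit baseline use gives, for opposite directions:

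- 10% dropout: 2 × 0.6 × 0.10 × 0.5 × 0.94 = 0.06, up to 2 × 0.6 × 0.10 × 0.9 × 0.90 = 0.10 SD.
- 20% dropout: 2 × 0.6 × 0.20 × 0.5 × 0.95 = 0.11, up to 2 × 0.6 × 0.20 × 0.9 × 0.93 = 0.20 SD.

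**Simulation of the rule** (4,000 trials per setting) agrees to within 0.01 SD, which rounding of D and simulation error explain:

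| Dropout linked to baseline use | Baseline use omitted | Bias, 10% dropout | Bias, 20% dropout |
|---|---|---|---|
| Opposite directions by arm | 90% to 95% | 0.05 to 0.09 SD | 0.11 to 0.19 SD |
| One arm only | 57% to 91% | 0.02 to 0.04 SD | 0.04 to 0.07 SD |
| Same in both arms | 4% to 79% | about 0 | about 0 |

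The standard error of the contrast is about 0.22 to 0.24 SD. If heavier users leave SBIRT-PN, the bias favours SBIRT-PN. In the opposite-direction case the rate chi-square is significant in only 5% to 6% of trials. With arm and baseline use always in the imputation, bias is within 0.01 SD of zero in every setting.

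**Does step 3 repair it?** If arm is in the imputation and baseline use is not, each missing value becomes its arm's completer mean, so the imputed 6-month contrast equals the completers' contrast and the two agree by construction. If arm is left out too, both are still biased the same way: −0.21 SD (completers) and −0.16 SD (imputed) in the strongest opposite-direction setting at 20% dropout. For change from baseline, the completers' bias follows ρ − 1 = −0.4 instead of 0.6, so its sign flips: about +0.10 SD against −0.14 SD for the imputed analysis (opposite directions, 20% dropout, odds ratio 2 per SD). The two then disagree, but neither is unbiased.

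**The case against.** The strongest reply is that the bias is conditional. A reader might infer that the Aim 3 contrast will be biased; the documents do not support that. If dropout depends on baseline use in the same way in both arms, the contrast is unbiased whether or not the screen selects it. Nothing in the protocol suggests mirror-image dropout, and 20% is its stated maximum, not its expectation. That stands.

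A reader might also infer that a by-arm test would be the cure. It would help in the mirror-image case: at 20% dropout an interaction test detects the pattern in 43% to 92% of trials, while the overall screen selects baseline use in 5% to 7%. For a link in one arm only it does no better than the overall screen (14% versus 14%, up to 38% versus 37%, at 20% dropout). The remedy is to stop letting a test choose the variables.

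Nor do the documents say that two non-significant checks will be taken as proof of harmless dropout. Step 3 runs whatever they show and may expose a discrepancy, though it does not cure one.

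The threshold is borrowed, and the text says neither that the screen ignores arm nor that no other variable may enter. A looser threshold helps somewhat: for a strong one-arm link (odds ratio 3) at 20% dropout, omission falls from 58% at .05 to 45% at .10. With opposite directions it is still 72% to 79% at .20. If arm is left out of the imputation, a true effect also shrinks, which can offset the bias by chance; that is no protection.

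Finally, Aim 3 is secondary in a feasibility pilot, and the feasibility and acceptability endpoints are untouched.

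**Conclusion.** The concern holds in conditional form. The plan lets a weak screen decide which variables enter the imputation, and the screen does not target dropout that differs by arm. If such dropout occurs, the worst case considered is 0.19/0.24, about 0.8 of a standard error, at the 20% maximum. At the expected 10% with opposite directions it is at most 0.09/0.22, about 0.4. A one-arm link costs at most 0.07/0.24, about 0.3. If the pattern is common to both arms the cost is nil.

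These sizes rest on the assumed correlation, threshold and dropout gaps, and on a simulation without a 3-month value, which some dropouts may have. They apply to the drug-use contrast. The treatment-engagement comparison is affected only if baseline use also predicts engagement. The change is worth making because the bias is avoidable at almost no cost, not because it has been shown to be present.

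**What to change.** In protocol section 17.0, and in a missing-data paragraph added to the SAP, replace the selection rule with a fixed imputation model. For every Aim 3 outcome, always include arm, site, age, the baseline value of that outcome, and its 3-month value when observed, whatever the dropout tests show. Variables found related to dropout may be added, but should not decide whether these enter.

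For step 1, report dropout by arm as a difference with a 95% confidence interval, and show baseline drug use of dropouts and completers separately within each arm. State that a non-significant chi-square is not evidence that dropout was unsystematic. Keep the completers comparison as a description, not as a safeguard.

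The cost is wording and a few more parameters in the imputation model. No new data are needed.

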To examine ratings of acceptability, we will use the overall acceptability score and percentage of acceptability. Overall acceptability will be assessed by summing ratings from the 10-item questionnaire to provide a total intervention acceptability score for the intervention, such that acceptability scores for the intervention could range from 10 (low acceptability) to 50 (high acceptability). The intervention will be considered to have acceptability if 80% of the participants rank the intervention as acceptable (i.e., 4 or higher) on 80% or more of the scale items. We will then examine each question of the Acceptability Questionnaire separately to determine strengths and weaknesses of the intervention.

Aim 2a and 2b (Acceptability): Acceptability scores will be calculated for all participants as listed above to determine overall acceptability of the SBIRT model. Sub analyses will be conducted for disease type and HIV x age using calculations listed above. Acceptability will be examined by disease type HIV vs. non-HIV. Acceptability will also be examined for HIV only by younger (≤ 49) versus older (≥ 50).

Aim 3: We will clean the data, examine variable distributions, compute descriptive statistics, examine outliers, and examine the effectiveness of randomization prior to analyses of specific aims to ensure the underlying assumptions of normality and equal variance have not been violated. Before testing each secondary outcome, we will examine whether intervention and control group participants differ on potential confounding variables at study entry. We will control for a variable if it differs by condition on the outcome variable being tested in that analysis at $p < .05$. Using chi-square (or t-test for continuous variables) we will examine the associations between the dependent variables and relevant demographic variables. All analyses will employ an intent-to-treat approach.

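### The planned completers-versus-imputed comparison cannot show whether unseen use among patients lost in one arm biases the Aim 3 result, and no planned analysis can

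*Protocol*

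**What the plan says.** The Missing Data paragraph of protocol Section 17.0 has three steps.

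- **Step 1:** "the dropout rates will be compared across the groups with chi-square analyses to assess systematic differences due to condition".
- **Step 2:** "demographic and dependent variables will be examined for their relationship to dropout". The variables found to be related are then used to fill in missing values with an SPSS routine.
- **Step 3:** "comparison of the completers vs. imputation analyses will yield an additional estimate of the effect of dropouts on hypothesis tests".

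On the expected extent of loss, Section 25.0 (Retention) says "we anticipate a 10% dropout rate with a maximum dropout rate of 20% by time 3". With assessments at baseline, 3 and 6 months, time 3 is read here as month 6.

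The SAP has no missing-data text, but it keeps the statement "All analyses will employ an intent-to-treat approach". Neither document plans an analysis in which patients lost to follow-up may differ from observed patients in ways that the observed data do not predict.

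**The concern.** Step 3 is offered as an estimate of what dropout does to the hypothesis tests. The completers analysis is unbiased if dropout is unrelated to use. The imputed analysis is unbiased if dropout is unrelated to use given the variables in the imputation model. Neither uses information on the use of those who left. If leaving goes with use heavier than the observed data predict, and this happens more in one arm, both estimates can be wrong. Adding randomised arm to the imputation does not cure this.

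The protocol's own account makes such a pattern plausible. Section 3.0 links misuse to poorer engagement in HIV care and suggests that peer navigators may improve treatment engagement. Section 5.0 assigns a navigator during the SBIRT-PN session. Section 25.0 relies partly on clinic return visits to re-engage participants. Loss may therefore depend on use, and differently by arm. The direction cannot be known in advance. At stake is how the Aim 3 test on drug-use days is read.

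**Working it through.** **Inputs from the documents.** Sample size: "Participants will be 90 patients recruited through DOH Columbia County and CAN Community Health". Allocation is in blocks of 4 by site "to ensure equal numbers are assigned to each condition by site", so about 45 per arm. Dropout is 10% expected and 20% at most. Completers: 90 × 0.9 = 81 (about 40 per arm) or 90 × 0.8 = 72 (36 per arm).

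**Assumed, because the documents give no value.** The excess use among those lost, the standard deviation and the correlations between visits. The plan states no power or effect size for this outcome, so there is no figure of its own to reproduce.

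**1. Size of the shift.** If patients lost in one arm use δ more days than predicted, and those lost in the other arm do not, the month-6 arm difference moves by dropout share × δ.

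| Dropout | δ = 5 days | δ = 10 days |
|---|---|---|
| 10% | 0.10 × 5 = 0.5 | 0.10 × 10 = 1.0 |
| 20% | 0.20 × 5 = 1.0 | 0.20 × 10 = 2.0 |

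In a simulation with 45 per arm, 20% dropout and use truncated to 0–30 days, the standard error of the completers difference was about 1.8 days. The shifts are then 0.5/1.8 = 0.28, 1.0/1.8 = 0.56 and 2.0/1.8 = 1.11 standard errors. With an assumed SD of 9 days and 36 completers per arm, the standard error is 9 × √(2/36) = 2.1 days, and the ratios are a little smaller.

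**2. What step 3 would show.** A second simulation used 45 per arm, SD 9 days, correlations 0.5–0.6, no effect among retained patients and 1,500 runs per scenario. Multiple imputation used arm, baseline and month-3 use. The protocol does not promise arm or month-3 use as predictors, so this is generous to the plan. Differences are the affected arm minus the other, in days.

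| Scenario | True | Completers | Imputed |
|---|---|---|---|
| A1: random 20% dropout, those lost in one arm use 5 more days | 0.95 | -0.03 | -0.05 |
| A2: as A1, 10 more days | 2.10 | 0.13 | 0.10 |
| A3: as A2, 10% dropout | 1.06 | 0.07 | 0.07 |
| B: dropout in one arm depends on observed month-3 use | -0.05 | -1.30 | -0.08 |
| C: dropout in one arm depends on unseen month-6 use | 0.05 | -2.00 | -1.19 |

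In A the two analyses agree on average and both miss the difference. In A1 and A2 they reach the same significance conclusion in 96–97% of runs. In B they disagree and imputation is right, so the comparison does its job. In C they differ by 2.00 - 1.19 = 0.81 days and both are biased. The truncated 0–30 day simulation gave the same picture as A: with 5 or 10 extra days among TAU dropouts, the true difference was -0.94 or -1.89, and both analyses were within 0.03 of zero.

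**3. The other two steps.** At 45 per arm and two-sided 0.05, the chi-square on dropout rates has 26% power for 10% versus 20%, 58% for 5% versus 20%, and 66% for 10% versus 30%. It cannot detect equal rates with different reasons for leaving. The search for predictors of dropout sees only observed variables.

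**The case against.** A reader might infer that step 3 is the only check on dropout, that its two analyses rest on one assumption, and that they must therefore agree. The documents support none of these. Two other dropout checks are planned, and step 3 is itself called additional. Imputation needs a weaker condition than the completers analysis, so their comparison is informative when dropout follows observed variables (scenario B). Agreement in scenario A follows from making dropout random before adding extra days. When dropout depends on unseen use, the two diverge (scenario C). That divergence would be some warning, although it would not show that the imputed result is also biased.

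A reader might also infer that the arms are unmasked and that agreement would be reported as proof of robustness. The documents do not describe masking, and the protocol makes no explicit robustness claim.

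The larger shifts depend on 20% dropout or on 10 extra days, with all the excess in one arm. At the anticipated 10% the shift is 0.5 to 1.0 days, about a quarter to just over half of one standard error. The outcome is secondary, the trial is a 90-patient pilot, and Section 25.0 plans substantial retention work. All this stands and lowers the severity. It does not supply the missing analysis: no step lets those lost differ in unseen use, and Aim 3 is still tested by F and p values.

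**Conclusion.** The point holds in limited form. Step 3 is the only planned check of the Aim 3 treatment result against dropout, and it addresses only dropout related to observed variables. It is not an estimate of the effect of dropout in general. Agreement does not exclude bias from unseen use, and disagreement does not show that the imputed result is sound.

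Under the assumed excess of 5 to 10 days in one arm, the error is 0.5 to 1.0 days at 10% dropout and 1.0 to 2.0 days at 20%, in either direction depending on the arm. These sizes rest on assumed excesses, on equal dropout in both arms and on the simulation's spread. They illustrate scale and do not predict this trial's bias. The primary feasibility and acceptability outcomes are outside this point. It is a cheap improvement of low severity.

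**What to change.** In the SAP, add missing-data text with one prespecified sensitivity analysis for drug-use days. After imputation, add a range of values (for example 0, 2, 5 and 10 days on a 30-day measure) to imputed values, separately by arm, with a cap at the length of the recall window. Four values in each arm give 4 × 4 = 16 combinations. Report the arm difference for each, and the shift at which the Aim 3 conclusion changes.

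Before setting the values and the cap, reconcile the recall window. Protocol Section 4.0 describes a measure over the prior 30 days, while Section 17.0 and the SAP analyse drug-use days over the past 3 and 6 months.

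Reword step 3 so that the completers comparison is described as a check on dropout related to observed variables.

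The cost is a few lines of SAP text, repeat runs on data already collected and one more table. The downside is that the result may look less certain.

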18.0 Provisions to Monitor the Data to Ensure the Safety of Subjects*

N/A

19.0 Provisions to Protect the Privacy Interests of Subjects

To ensure confidentiality, all information will be coded so that it cannot be associated with any individual. A master sheet, with individual names and their respective code numbers will be kept in a locked file that can be accessed only under supervision of the PI. All data entered into the computerized database will be identifiable by subject code number only. No one outside of the lead research team will have access to records identifying participants' names at any time. The information gathered will be used only for scientific, educational, or instructional purposes.

Any computer files with identifying data, such as subject logs needed to match data to names over time, will be protected by multiple passwords. During the analysis of the data, all identifying information with the exception of the subject identification number is removed from the data.

Discomfort with Procedures or Disclosure Safeguards

During the course of participation in the research, a participant may have questions about the assessment procedure. A project staff member or interventionist will be available to answer questions. To prevent discomfort or embarrassment, staff are trained in building rapport and skillful interviewing. Participants are informed prior to the assessment that they may choose to skip any questions or procedures they find uncomfortable. If any individual becomes overly distressed or distraught, the assessment will be stopped immediately and a staff clinician will talk privately with the affected individual(s) and appropriate referrals will be made, as needed.

